10.7. Exploratory analyses

Following discussions with Greater Change, we are interested in whether effects are concentrated elsewhere in the distribution from the mean of our outcome measures. For example, it is hypothesised either that people with higher than average housing stability might benefit from the intervention, or that people with lower housing stability might do so. However, these hypotheses are not sufficiently well articulated at this stage to form a part of the Theory of Change, or to specify which has the larger effect. To investigate these hypotheses, we will conduct quantile regressions specified in the same way as our main analyses, evaluating the impact of the intervention at the 25th and 75th percentile.

10.8. Interim Analyses and Data Monitoring (If applicable)

We will conduct an interim analysis based on the data collected at midline - 6 months after randomisation. This analysis will follow the same specification as our primary analysis at 12 months. Sensitivity analyses using outcome imputation will not be possible at this stage but will be carried out once endline data have been collected.

10.9. Missing data

Description of Missing Data Patterns

The issue is that those who do not respond to the surveys at endline are likely to be different to those who do, i.e., cases are likely to be either Missing at Random (MAR), if all missingness is correlated to observable covariates, or Missing Not At Random (MNAR), if missingness is correlated with unobservable factors.

Identification of the missingness pattern will be achieved by regressing all available covariates on the likelihood of missingness using a binary logistic regression to see whether covariates predict missingness on outcomes, as specified in the CHI Guidance. If covariates predict missing outcome data well, this suggests that the outcome is MAR .

Where reasons for missingness are known and imply the data are Missing Completely at Random (MCAR), we will conduct complete case analysis.

Handling Missing Data

Our main analysis will be on the basis of complete cases. However, it is likely that there will be greater than 5% attrition for the post-treatment survey waves, which will impact statistical power and

also mean that in some cases we may be comparing outcomes from different samples (e.g. if people who do not respond at 6 months then respond at 12 months and vice versa). This is in line with CHI's statistical guidance.

We will therefore rerun the analysis with missing outcomes imputed. As previously stated, if covariates predict missing outcome data well, this suggests that the outcome is MAR. In this instance, we will add outcomes at previous time points as auxiliary variables, alongside any covariates predictive of missingness into the analytical specification and re-run the analysis, comparing the treatment estimate with the analysis as specified, and the analysis with additional covariates and past outcomes that predict missingness included. If outcomes are MNAR, then neither complete case nor imputation is likely to yield unbiased estimates of the treatment effect. In this case, we will run a range of imputation models, including multiple imputations within the treatment condition and the last observation carried forward (LOCF) and report on how much the treatment estimate changes across different imputation approaches.

Covariates are collected prior to randomisation, and therefore any missingness is less likely to be correlated with treatment or other variables (and hence more likely to be Missing Completely At Random). Thus, a complete case analysis will be used where there is a non-response on covariates. Implications of the missing data analysis will be discussed in the final report.

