Where 1{.} is an indicator function that is equal to 1 if its argument is true and 0 otherwise.

Then the outcome variable is regressed on $E(d_i|B_i)$ with an OLS regression of the form:

$$Y_{ipt} = \alpha + \beta_1 Y_{ip0} + \beta_2 E(d_i | B_i) + \beta_3 X_i + \beta_4 P_p + u_i$$

Where the CACE estimator is β_2

Outcome imputation

We anticipate attrition between baseline, midline and endline data analysis. We will conduct missing data analysis as described below in 10.9, but given that every participant will complete the baseline survey, we primarily expect attrition in terms of outcomes, which will not be imputed under the missing data analysis. However, we will include sensitivity analysis which imputes outcomes between the two post-treatment data points where participants have missing data for one of these points but not the other. As such, if someone is missing data from midline but completes the endline data collection, we will impute their midline outcome measure as their endline outcome, and vice versa.

If exploratory analysis of the missingness mechanism satisfies the MAR assumption, the imputation of these points will be conducted with a dataset that incorporates all three time points to allow for the maximisation of all observed information in the process of imputation.

Following imputation, analysis will be conducted as previously described, for each post-treatment time point separately.

 For the main analyses, our primary outcome measure will be how many days out of the 360 after randomisation that a person is in secure accommodation. This measure will combine the measurement

taken at six months (midline) and that at 12 months, each of which will capture the prior 180 days. When someone completes the endline data but not the midline, they will be asked to recall the last 360 days. As a sensitivity analysis, we will conduct analysis just using the 180 days prior to the endline data collection as an outcome measure.

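### Section 10.9 reads covariate prediction of missingness as evidence of MAR, and no named analysis tests the complete-case result over a range of informative dropout

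*Protocol*

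**What the plan says.** Section 10.9 fixes the primary analysis set: "Our main analysis will be on the basis of complete cases". It then proposes to identify the missingness mechanism by "regressing all available covariates on the likelihood of missingness using a binary logistic regression to see whether covariates predict missingness on outcomes". The stated inference is "If covariates predict missing outcome data well, this suggests that the outcome is MAR". No cut-off for good prediction is given, and poor prediction is not assigned to any mechanism.

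What follows depends on the label:

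- **MAR.** The rerun is described as "we will add outcomes at previous time points as auxiliary variables, alongside any covariates predictive of missingness into the analytical specification", and its treatment estimate is compared with that of the planned model.
- **MNAR.** The section concedes that "neither complete case nor imputation is likely to yield unbiased estimates of the treatment effect". It then says "we will run a range of imputation models, including multiple imputations within the treatment condition and the last observation carried forward (LOCF"), and promises to report how far the estimate moves across approaches.

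Section 10.6 adds a carry-over between the two follow-up waves: "we will impute their midline outcome measure as their endline outcome, and vice versa". It allows an imputation using all three time points if exploratory analysis is judged to satisfy MAR, so the same condition appears a second time.

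For missing baseline values, section 10.9 says "a complete case analysis will be used where there is a non-response on covariates".

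**The concern.** MAR means that, given what was observed, missingness does not depend on the value that was not observed. A regression of missingness on observed covariates contains no information on that dependence. A strong fit shows that the data are not MCAR with respect to those covariates. It is equally compatible with MAR and with MNAR.

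The inference matters because a good fit leads to a rerun that is again valid only under MAR, and the methods listed for MNAR are then not called for. Even if they are run, multiple imputation within arm (as named, with no departure from MAR specified) rests on the same assumption as the complete-case model. LOCF replaces it with one other fixed assumption. Neither shows how strong informative dropout would have to be to change the conclusion.

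The trial is exposed to this. Its main outcome is days in secure accommodation, collected online or by telephone from people recruited in temporary accommodation, so losing contact and losing housing may well go together. Section 10.9 itself expects non-responders to differ from responders. Loss may also differ by arm: section 8.2 uses support workers to chase non-responders where possible, and under section 4.1 caseworkers have extra budget-related contact with treated participants.

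**Working it through.** **Inputs.** Section 9 and Table 7: two-sided alpha 0.05, power 0.8, pre/post correlation 0.6, 360 randomised, 270 effective at 25% attrition and 234 at 35%. Section 5.2: 1:1 allocation.

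**1. Reproduce the plan's MDES.** SE = sqrt((1 − 0.6²) × 4 / N) and MDES = (1.960 + 0.842) × SE.

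- N = 360: 0.2363 (stated 0.236)
- N = 270: 0.2728 (stated 0.273)
- N = 234: 0.2930 (stated 0.293)

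The stated figures are correct and are not at issue.

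**2. How much informative dropout would change the conclusion?** Let d be the dropout share in an arm, and δ the mean departure of that arm's dropouts from their MAR prediction, in outcome SDs. Then

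effect in all randomised = complete-case estimate + d_T·δ_T − d_C·δ_C.

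With equal attrition the correction is d × (δ_T − δ_C). Hold the SE at its planned value and take an estimate equal to the MDES of the scenario.

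- 25% attrition: the significance limit is 1.96 × SE = 0.1909. Significance is lost at a difference of (0.2728 − 0.1909) / 0.25 = 0.33 SD. The effect reaches zero at 0.2728 / 0.25 = 1.09 SD.
- 35% attrition: the limit is 0.2050. Significance is lost at (0.2930 − 0.2050) / 0.35 = 0.25 SD. The effect reaches zero at 0.2930 / 0.35 = 0.84 SD.

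For a beneficial estimate, the damaging direction is intervention-arm dropouts doing worse than predicted by more than control dropouts do. The opposite direction would mean that the complete-case estimate understates benefit.

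**3. Can the regression tell the mechanisms apart?** Simulation of 400 trials per mechanism: N = 360, true effect 0, correlation 0.6, 25% missing on average. Missingness was regressed on baseline and arm. The mechanisms are illustrative assumptions. No midline was simulated, so LOCF here carries the baseline forward.

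| Mechanism | AUC | Baseline significant | Bias: complete case | Bias: MI within arm | Bias: LOCF | Complete-case type I error |
|---|---|---|---|---|---|---|
| MAR, strong baseline dependence | 0.82 | 100% | 0.003 | 0.001 | 0.003 | 4.0% |
| MNAR, same baseline dependence, plus outcome dependence of opposite sign by arm | 0.81 | 100% | 0.106 | 0.136 | 0.055 | 19.5% |
| MCAR | 0.54 | 4% | −0.006 | −0.007 | −0.006 | 4.8% |
| MNAR, outcome only, opposite sign by arm | 0.54 | 6% | 0.206 | 0.207 | 0.091 | 59.3% |
| MNAR, outcome only, same in both arms | 0.65 | 99% | −0.006 | −0.005 | −0.004 | 4.5% |

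The first two rows are indistinguishable to the diagnostic and would both be read as MAR, yet only one is unbiased. Rows three and four are likewise indistinguishable. Imputation within arm gave no protection under either arm-dependent MNAR mechanism. The last row shows that outcome-dependent dropout acting alike in both arms did little harm here, so the risk lies in differences between arms.

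**The case against.** Much can be said for the plan.

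- **The primary analysis does not depend on the diagnostic.** It is complete-case whatever the regression shows. Only the rerun in 10.9 and the three-wave imputation in 10.6 are conditional. This stands.
- **The list is open and not wholly MAR-based.** It is introduced as including the two methods. LOCF is a non-MAR assumption, and the 10.6 carry-over has no MAR condition. A reader might infer that informative dropout is never examined; the text does not support that. But each is a single fixed assumption, and the 10.6 carry-over reaches only people seen at one of the two follow-up waves.
- **Poor prediction is not equated with MNAR.** A reader might infer a two-way switch. The protocol states only the MAR half and leaves open how MNAR would be concluded.
- **The protocol is candid.** It admits likely bias under MNAR and promises to discuss implications. That does not supply a result to discuss.
- **A statistical analysis plan may add methods, and the diagnostic follows cited guidance.** Neither removes an incorrect inference that the protocol itself states.

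A reader might also want a definite bias. With 20% and 30% attrition in the intervention and control arms and dropouts 0.5 to 1 SD below prediction in both, the formula gives 0.05 to 0.10 SD; with 25% in each arm and the shift in controls only, 0.125 to 0.25 SD. All these inputs are invented, and all four cases understate benefit. They do not establish a size or a direction for this trial.

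**Conclusion.** The point holds in a limited form. Section 10.9 draws an inference that its diagnostic cannot support and lets it choose the sensitivity rerun. The methods named in 10.6 and 10.9 do not test the complete-case result over a range of informative-dropout assumptions.

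The size is given as thresholds: a between-arm difference in departure of about 0.33 SD at 25% attrition, or about 0.25 SD at 35%, removes significance from an estimate at the MDES. This assumes equal attrition by arm, the planned correlation of 0.6 and an unchanged standard error. The real departure is not in the documents, so this is not a finding that the result will be biased.

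The covariate rule is a minor matter. Annex C allows don't-know or not-applicable answers, so a baseline housing-satisfaction score could be incomplete. But age already has a prefer-not-to-say category, and the housing history in Annex B accepts best guesses. A reader might infer a material loss of power; the documents give no frequency from which to calculate one.

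**What to change.** In section 10.9, keep the logistic regression as a description of who is missing and delete the inference to MAR. Remove the matching condition in 10.6. Whatever the regression shows, always run:

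1. multiple imputation by arm, with baseline and midline outcomes as auxiliaries in the imputation model;
2. a delta-adjusted tipping-point analysis that shifts imputed outcomes in steps, separately by arm and in both directions, and reports the shift at which the conclusion changes.

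LOCF may stay as a secondary check but should not be the only non-MAR analysis named.

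Optionally, where a baseline outcome score is missing, keep the randomised participant by mean imputation with a missing indicator.

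The cost is rewording and a little more analysis work. No new data are needed, and the sample size and primary model are unchanged.

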The organisation delivering the model is Greater Change. They work together with local partner charities to ensure that clients receive additional non-financial support alongside funding in a timely manner. In contrast to other conditional funds, Greater Change does not have pre-set eligibility and spending criteria. The conditional funds are used to support the flexible and sustainable plan created and agreed upon ahead of time by the support worker and the service user.

This project will compare the use of personalised budgets that are managed by a caseworker and control groups under business-as-usual.

We assume that, on average, participants in the treatment group will receive funds of £4,000.

Participants are expected to spend their allocated funds within a three-month period. However, on a case-by-case basis, participants will be permitted to receive the intervention even in the face of necessary spending extensions, these cases will not be treated as non-compliant nor excluded from analysis. These extensions are in response to operational realities and are critical to the successful running of the trial. They also enable the intervention to more closely reflect how it would operate outside a trial context. The reasons for granting extensions can be grouped into two categories:

- Staff-related delays: including administrative expenditure delays, annual leave of case workers, and reduced partner engagement with participants.
- Participant-related delays: including hospitalisation, rehabilitation, custody, bereavement, or other extenuating personal circumstances.

Control

Participants will retain the same support as they would otherwise have received, including access to smaller personalised budgets or grants, as they would have had in the absence of the trial.

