6.4. Trial Flow Diagram

7. OUTCOME MEASURES

7.1. Primary Outcome

Definition

Following the above Theory of Change, we are primarily interested in measuring potential changes in participants' housing outcomes. Our primary outcome measure will therefore be the number of days out of the 360 days after they were randomised that a person is in secure accommodation. This main analysis will be conducted after the endline data collection 12 months after randomisation.

For this purpose, we will be assessing participants' housing stability and their perceived housing quality and satisfaction (see Annexes B and C). We deem it necessary to complement participants' housing history with questions regarding other relevant aspects of housing such as 1) affordability, 2) choice, independence, privacy, 3) suitability.

Instruments

Questions concerning participants' housing history have been adapted from the Residential Time Line Follow Back Inventory (Tsemberis, S. et al. (2007; see Annex B). Modifications have been mainly made to simplify and adapt the questions to the UK context. Similarly, minor modifications have been made to the OMRA tool, which includes questions about general satisfaction with housing, affordability, choice, independence, and privacy, and suitability.

When is it measured

Participants' data used in this analysis will be collected at three time points: baseline (prior to randomisation) and endline (12 months after randomisation). We will also collect these measures at 6 months after randomisation, and this will be included in our interim analyses.

 For whom is it measured All participants in the treatment and control groups will be surveyed by IFF.

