10.3. Primary Analyses

Analytical approach

Our main analytical approach for our primary analysis is regression analysis, which will be conducted on an intention-to-treat, complete cases basis. For our main housing outcomes, housing stability and perceived housing quality and satisfaction, measured via Residential Time Line Follow Back Inventory and the OMRA tool, we will conduct a linear regression, evaluated at the mean. Formally, this will be an autoregressive (AR-1), model, specified as:

$$Y_{ipt} = \alpha + \beta_1 Y_{ip0} + \beta_2 B_i + \beta_3 X_i + \beta_4 P_p + u_i$$

Where:

 Y_{ipt} is the value of the respective outcome measure (housing stability and perceived housing quality and satisfaction), for participant i at time t (endline in the primary analysis), referred by charity partner p.

 α is a regression constant

 Y_{i0} is the baseline value of the outcome for participant i in charity partner p.

 B_i is a binary treatment indicator set to 1 if participants are treated and zero else.

 X_i is a vector of participant demographic characteristics including gender (operationalised as a trinary variable) and age (operationalised as a categorical variable with 7 values including prefer not to say).

 P_p is a vector of charity partner fixed effects, reflecting that charity partner is a stratification variable.

 u_i is an error term.

This analysis will be conducted with two values of the time indicator, at the midline and endline data collection points, in both cases using the baseline data at time 0 as a control. Uncertainty will be reported through confidence intervals at p-values. We will report the binary indicator of whether the treatment effect is statistically significant, as well as present the p-value continuously and the confidence intervals.

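### The MAR re-analysis in section 10.9 puts the midline outcome into the endline regression, so its treatment coefficient answers a different question and cannot serve as a check on attrition

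*Protocol*

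**What the plan says.** Section 10.3 defines the main model: a linear regression of the outcome on treatment, its baseline value, gender, age and charity partner. It is fitted at midline and at endline, "in both cases using the baseline data at time 0 as a control". It is an intention-to-treat, complete-case analysis.

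Section 7.1 defines the housing outcome as "the number of days out of the 360 days after they were randomised that a person is in secure accommodation". Section 10.6 explains that this count combines the measurement "taken at six months (midline) and that at 12 months, each of which will capture the prior 180 days". Section 7.1 adds: "We will also collect these measures at 6 months after randomisation, and this will be included in our interim analyses".

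Section 10.9 expects attrition and says: "We will therefore rerun the analysis with missing outcomes imputed". If covariates predict missing outcomes well, which the protocol takes as a sign of MAR, then "we will add outcomes at previous time points as auxiliary variables, alongside any covariates predictive of missingness into the analytical specification". The analysis is re-run, and the treatment estimate as specified is compared with "the analysis with additional covariates and past outcomes that predict missingness included".

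Section 10.6 (outcome imputation) describes the MAR case differently. For participants missing one of the two follow-ups, the imputation draws on data from all three time points, and the analysis is then run as already described, separately for each follow-up.

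**The concern.** The baseline outcome is already in the model. For the endline analysis, the only earlier outcome left to add is midline, which is measured after randomisation. Section 5.2 says "Participants are expected to spend their allocated funds within a three-month period", with extensions possible, so midline can already carry part of the treatment effect. Holding it fixed removes that part from the treatment coefficient. For housing days the problem is sharper, because midline supplies the first 180 of the 360 days being explained.

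The comparison exists to show whether missing data have distorted the result. With midline in the regression, the two estimates would differ even if nobody were lost, so the comparison cannot do that job. With 25% attrition assumed in section 9.2, readers will look to this check. The step is also weak as a missing-data remedy: extra regressors alone recover no one whose endline outcome is missing.

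**Working it through.** **Notation.** M1 and M2 are secure days in the first and second 180 days, and Y = M1 + M2. Y0 is the baseline value and B is treatment. d1 and d2 are the effects of treatment on M1 and M2. s = d1/(d1 + d2). b is the within-arm slope of M2 on M1 given Y0.

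**Inputs from the protocol.** The 180 + 180 composition (10.6); baseline already in the model (10.3); pre/post correlation 0.6, two-sided alpha 0.05, power 0.80, effective N 270, MDES 0.273 (section 9, Table 7).

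**The plan's own figure.** MDES = (1.960 + 0.842) × √(4 × (1 − 0.6²)/N). This gives 0.236, 0.273 and 0.293 for N = 360, 270 and 234, matching Table 7.

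**Assumed inputs, not in the protocol.**
- s = 0.25 (effect grows linearly from zero), 1/3 (constant after a three-month delay: 90 of 270 days) or 0.50 (constant throughout).
- b = 0.375 if all pairwise correlations are 0.6: (0.6 − 0.36)/(1 − 0.36).
- b = 0.6 if correlation decays as AR-1 at 0.6 per wave: (0.6 − 0.6 × 0.36)/(1 − 0.36).
- b = 0.8 as a high value.

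**Algebra.** Regressing Y on B and Y0 gives d1 + d2. Regressing M2 on B, Y0 and M1 gives a treatment coefficient of d2 − b·d1. Using Y in place of M2 only adds 1 to the coefficient on M1 and leaves the treatment coefficient unchanged. The share removed is therefore

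1 − (d2 − b·d1)/(d1 + d2) = s(1 + b).

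| s | b = 0.375 | b = 0.6 | b = 0.8 |
|---|---|---|---|
| 0.25 | 34% | 40% | 45% |
| 1/3 | 46% | 53% | 60% |
| 0.50 | 69% | 80% | 90% |

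For illustration, take an assumed 30-day effect with b = 0.6. A 15 + 15 split returns 15 − 0.6 × 15 = 6 days. A 10 + 20 split returns 20 − 0.6 × 10 = 14 days.

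More than half is lost only when s > 0.5/(1 + b), that is, above 36%, 31% or 28% for the three slopes.

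**Simulation check.** With 400,000 simulated participants and no missing data, the retained shares were 0.66, 0.60 and 0.55 (s = 0.25), 0.53, 0.47 and 0.42 (s = 1/3), and 0.31, 0.20 and 0.10 (s = 0.50). These agree with the formula within simulation error.

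**Power, N = 270, true effect 0.273 SD, 3,000 replicates.** Each cell gives power without midline, then with midline.

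| s | all correlations 0.6 | AR-1 at 0.6 |
|---|---|---|
| 0.25 | 86% → 94% | 75% → 85% |
| 1/3 | 86% → 82% | 75% → 64% |
| 0.50 | 86% → 39% | 75% → 17% |

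The starting values differ from 80% because these structures imply a baseline correlation with the 360-day total of 1.2/√3.2 = 0.67 or 0.96/√3.2 = 0.54, not 0.6. Power can rise as well as fall, because midline also absorbs residual variance. Neither direction says anything about attrition.

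**Other outcomes.** For housing satisfaction and the secondary outcomes, midline is not a component of the endline value. The augmented coefficient is the endline effect minus b times the midline effect. If the two effects are equal, the share removed is b: about 38% to 80%.

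**The case against.** The strongest defence is that 10.9 means imputation. Its paragraph opens by promising imputed outcomes, auxiliary variables is the usual term for variables in an imputation model, and 10.6 sets out a MAR imputation using all three waves followed by the unchanged analysis. On that reading the bias does not occur. This makes the text ambiguous, but it does not remove the instruction: 10.9 names the analytical specification as the place for these variables and defines the comparison as a regression with and without them. Within 10.9, multiple imputation is named only for the MNAR branch. An analyst following 10.9 literally fits the wrong model.

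Some stronger readings are tempting but unsupported:
- *The step removes most of the effect.* This depends on s and b, which the protocol does not give. With a slowly building effect the loss is 34% to 45%.
- *Midline is half of the primary outcome.* This holds for housing days only, not for the satisfaction co-primary.
- *Everyone without a midline is dropped.* This follows only under a pure complete-case reading. Section 10.6 imputes a missing midline when endline is present, and otherwise relies on 360-day recall.
- *The main result is compromised, or the report would blame attrition.* The main analysis is the complete-case regression in 10.3. The step is conditional on covariates predicting missingness, and the protocol says only that implications will be discussed.

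Table 6 lists only secondary outcomes at midline, which might suggest there is no midline housing measure to add. Sections 7.1 and 10.6 and Annex B all say housing is asked at midline.

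**Conclusion.** The concern holds for the endline re-analysis as section 10.9 words it. Conditioning on midline changes the quantity estimated, from d1 + d2 to d2 − b·d1 for housing days, so a difference from the main estimate is not evidence about missing data. That conclusion is algebraic and needs only some effect before midline or some carry-over from it. The size rests on assumed inputs: a loss of about 34% to 90% for s between 0.25 and 0.50 and b between 0.375 and 0.8. Sections 10.9 and 10.6 also describe the MAR step differently. The primary complete-case estimate is untouched, and the midline analysis is unaffected because its only earlier outcome is baseline. This should be corrected before the endline analysis, but it is a fault in a robustness check and not in the main result.

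**What to change.** Reword the MAR step in section 10.9 to agree with 10.6:
- Use midline outcomes only as auxiliary variables in the imputation model, for example multiple imputation run by arm or with treatment included.
- Fit the unchanged section 10.3 regression to the imputed data and compare that estimate with the complete-case one.
- Allow only variables measured before randomisation to be added to the regression itself.

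The cost is a wording change and a little extra analysis code. No new data are needed.

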Annex C: PERCEIVED HOUSING QUALITY AND SATISFACTION

ASK ALL: BASELINE, MIDLINE AND ENDLINE

Introduction: Now I'd like to ask you about how you feel about the place you live in.

1f. Below are some statements about your housing situation. Please tick the box that best describes your current experience.

How satisfied are you about....

- 1. Your current housing in general (where you live now)
- 2. How affordable your housing is
- 3. The amount of choice you had selecting the place you live in
- **4.** How much control you have over who can come into the place you live in (e.g. children, pets and guests)
- 5. How long you will be able to live there
- 6. The amount of privacy you have in the place you live
- 7. The level of fairness and respect shown by your landlord (if applicable)
- 8. The suitability of the place you live in to meet your (or your family's) needs
- **9.** The condition of the place you live in (such as appliances, plumbing, things needing to be repaired)
- 10. The safety and security of your building

All responses on a 5-point Likert scale from 'Very dissatisfied' to 'Very satisfied', and DK/NA [Note: Statements in red could be excluded if needed].

Source: Modified version of the Housing Satisfaction and Quality scale

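### Dropping randomised participants with an outcome because a baseline covariate is missing loses precision that a one-sentence change would partly keep

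*Protocol*

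**What the plan says.** Section 10.9 gives the rule for covariates: "a complete case analysis will be used where there is a non-response on covariates". Its reason is that covariates are collected before randomisation, so that "any missingness is less likely to be correlated with treatment or other variables".

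Section 10.3 describes the main analysis as a regression "which will be conducted on an intention-to-treat, complete cases basis". The model has four adjustment terms:
- the baseline term, which "is the baseline value of the outcome for participant i in charity partner p";
- gender, with three levels;
- age, as a "categorical variable with 7 values including prefer not to say";
- charity partner fixed effects, "reflecting that charity partner is a stratification variable".

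Section 10.4 carries the same model to the four secondary outcomes. Section 5.2 has the survey script randomise each person when the baseline survey is submitted. Annex C offers a non-answer on every satisfaction item: "All responses on a 5-point Likert scale from 'Very dissatisfied' to 'Very satisfied', and DK/NA". Annex E offers the same on the wellbeing items, and Annex F has a refusal code for employment status. Section 15.4 says participants will be reminded that they may decline questions.

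The imputation plans in Sections 10.6 and 10.9 concern missing outcomes.

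**The concern.** Anyone with an unanswered baseline item is already randomised, and may well supply an endline outcome. Under the rule in Section 10.9 that outcome is not used. Nothing elsewhere in the protocol restores the participant, because the imputation analyses fill in outcomes and not covariates.

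Not every covariate can cause a loss. Age has its own non-disclosure level, and charity partner is known for everyone because randomisation is stratified on it. Losses would come from the baseline outcome, mainly on the satisfaction and secondary scales, and possibly from gender, since the protocol does not say whether its third level holds non-response.

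The reason given in Section 10.9 supports the absence of bias between arms. It does not call for deletion: missingness fixed before randomisation is equally the setting in which mean filling with a missing indicator is valid in a randomised comparison, and that keeps more information. The plan already takes this approach for age.

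The stake is precision. The 270 behind the planning figure allows for outcome attrition only (Section 9.2), and Section 9.1 says the sample is capped by funding, so lost participants cannot be made up by recruiting more.

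**Working it through.** **Inputs from the protocol.** 360 randomised 1:1; 25% attrition, leaving 270; two-sided alpha 0.05; power 0.8; pre/post correlation 0.6 (Sections 5.2, 9.1 and 9.2, Table 7).

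**Reproducing the plan's figures.** MDES = (1.960 + 0.842) × √(1 − 0.6²) × √(4/N) = 2.8016 × 0.8 × √(4/N).
- N = 360: 0.2363 (stated 0.236)
- N = 270: 0.2728 (stated 0.273)
- N = 234: 0.2930 (stated 0.293)

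All three agree. Power at 0.273 with N = 270 is 80.1%.

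**Assumption.** Let m be the share of outcome responders with a missing covariate. The protocol gives no value, so a range is shown.

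**Under the plan.** N becomes 270 × (1 − m) and the residual variance stays at 0.64. For m = 10%: N = 243, MDES = 2.8016 × 0.8 × √(4/243) = 0.288.

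**With everyone kept, baseline outcome missing.** N stays at 270. Those without a baseline value contribute unadjusted variance, so the residual variance is (1 − m) × 0.64 + m × 1. For m = 10%: 0.9 × 0.64 + 0.1 = 0.676, and MDES = 2.8016 × √0.676 × √(4/270) = 0.280.

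| m | N under plan | MDES, plan | MDES, kept | Power at 0.273, plan | Power at 0.273, kept |
|---|---|---|---|---|---|
| 2% | 265 | 0.276 | 0.274 | 79.3% | 79.6% |
| 5% | 256–257 | 0.280 | 0.277 | 78.0% | 79.0% |
| 10% | 243 | 0.288 | 0.280 | 75.8% | 77.9% |
| 20% | 216 | 0.305 | 0.288 | 70.8% | 75.8% |

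**With everyone kept, only a demographic missing.** If demographics add no precision (an assumption), the residual variance stays at 0.64 and N at 270, so MDES stays at 0.273 for any m.

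**Share recovered when the baseline outcome is missing.** At 5%, the loss is 0.2799 − 0.2728 = 0.0071 and retention recovers 0.2799 − 0.2766 = 0.0033. At 10%, the loss is 0.2876 − 0.2728 = 0.0148 and retention recovers 0.2876 − 0.2804 = 0.0072. That is about half in each case.

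**Check on bias.** A simulation with 270 participants, a true effect of 0.273 and 4,000 repeats per setting compared deletion with mean filling plus an indicator. Missingness was either purely random or dependent on the baseline value. Mean estimates were about 0.272 to 0.275 for both methods in every setting. Power, deletion against retention, was about 78% against 78–79% at m = 5%, 75–76% against 78% at 10%, and 70–71% against 75–77% at 20%.

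**The case against.** The strongest defence is that the rule is valid. Deletion on data fixed before randomisation leaves the arm comparison unbiased, and Section 10.3 openly declares a complete-case basis. This stands. A reader might infer that the rule breaks the intention-to-treat principle or biases the effect. The documents do not support that: the deletion cannot depend on arm, and the simulation shows no bias even when missingness depends on the baseline value.

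The second defence is that few people may be affected. Enrolment requires baseline data (Section 6.3), and Section 10.6 expects everyone to complete the baseline survey. The housing history in Annex B, from which the days in secure accommodation are derived, lists no non-answer option and invites best guesses. One unanswered satisfaction item makes a scale score missing only if the scoring rule says so, and that rule may sit in an SAP that is not shown. People who skip baseline items may also be among those lost at endline, in which case the two losses overlap. All of this stands as a limit on size. It does not defend the rule itself: completing a survey is not the same as answering every item, and Section 10.9 itself provides for covariate non-response.

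Third, the fix does not undo the whole loss. A reader might set 0.280 or 0.288 against 0.273 and take the full gap as avoidable. That would hold only for a missing demographic. When the baseline outcome is missing, about half the gap remains.

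**Conclusion.** The point holds as one of efficiency. The rule discards randomised participants with observed outcomes when the baseline outcome, and possibly gender, is missing. It gains nothing over keeping them, and it leaves out part of the randomised set with outcomes. It does not bias the comparison between arms.

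The avoidable loss is small at plausible levels: about 1 point of power if 5% of outcome responders lack the baseline outcome, about 2 points at 10% and about 5 at 20%. These figures rest on assumed missing shares, on the protocol's correlation of 0.6, and on covariate gaps falling on top of the 25% attrition. That the effective sample will fall below 270 for this reason is therefore conditional, not established. The effect is more likely to be seen on perceived housing quality and satisfaction and on the secondary scales than on days in secure accommodation.

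**What to change.** Replace the covariate sentence in Section 10.9 with: *Participants with an observed outcome are kept. Missing baseline outcome values are set to the pooled baseline mean with a missing indicator, and missing categorical covariates form their own category, as age already does.* Keep complete cases on covariates as a sensitivity analysis.

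The mean should be taken over both arms together, so that the filled value does not depend on allocation. The cost is one sentence and a few lines of code, with no new data. The change can be made before analysis through the addendum route in Section 13.2.
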